3.7.2 Current Study (STML-401-0114)

Stage 1 of STML-401-0114 employed a traditional 3+3 design and has been completed. A total of 23 patients were enrolled in Stage 1, of whom 9 had BPDCN and 14 had R/R AML. SL-401 was investigated at doses of 7, 9, 12, and 16 µg/kg/day IV for up to 5 consecutive days every 21 days (i.e., a multi-cycle regimen). (Only patients with AML received SL-401 at doses of 9 and 16 µg/kg/day.) The maximum tested dose of SL-401 in patients with BPDCN was 12 µg/kg/day; an MTD was not identified in BPDCN.

A complete summary of all AEs attributed to SL-401, including DLTs seen in Stage 1 of the study, is available in the most recent version of the SL-401 Investigator Brochure.

An analysis of safety data available through 28 July, 2016, for 26 patients with BPDCN showed that, overall, 24 (92%) patients have experienced at least 1 treatment-emergent adverse event (TEAE), with 22 (85%) patients experiencing at least 1 ≥Grade 3 TEAE. The most common TEAE was transaminase elevation (either ALT increased [62%] or AST increased [58%]). Overall, 17 (65%) patients have experienced ALT increased and/or AST increased, with these events also being the most common ≥Grade 3 TEAE (each 54%), treatment-related TEAE (54%), and treatment-related ≥Grade 3 TEAE (50%). Transaminase elevations were largely transient and not dose-limiting.

Other most commonly reported TEAEs, regardless of relationship to study drug, were nausea and peripheral edema (each 46%); fatigue, hypoalbuminemia, and pyrexia (each 42%); chills (35%); and anemia and hyperglycemia (each 31%).

The frequency and type of TEAEs were similar between the 12 µg/kg/day and 7 µg/kg/day dose groups, with no indication of dose-relationship.

Twelve (46%) of 26 patients experienced at least 1 serious adverse event (SAE). The only SAEs reported for >1 patient were CLS, pyrexia, and respiratory failure (each 2 patients).

Please consult the most recent SL-401 Investigator Brochure for comprehensive and up-to-date information concerning the safety profile associated with SL-401.

An interim analysis of efficacy data was performed on 32 patients with BPDCN enrolled in the study through 29 August, 2016. Findings from this analysis, based on the Investigators' assessment of response, showed that of the 32 BPDCN patients evaluable for response, regardless of line or dose, the objective response rate (ORR) was 84%, and the CR rate (i.e., CR +CR with incomplete blood count recovery [CRi] + CR [clinical] with minimal residual skin abnormality [CRc]) was 56%. Of the 19 first-line patients (all doses) evaluable for response, the ORR was 95%, and the CR rate was 74%. Of the 16 first-line patients treated at 12 µg/kg/day

evaluable for response, the ORR was 100%, and the CR rate was 81%. Analysis of progression-free survival (PFS) showed that of the 16 evaluable first-line patients treated at 12 µg/kg/day, 11 were progression-free. This included 5 patients receiving ongoing SL-401 therapy for ~1-14+ months, all in CR (n=3) or PR (n=2), and 6 patients who sustained a remission while on SL-401 (CR [n=5]; PR [n=1]) and were then successfully bridged to SCT following ~2-6 months of SL-401 therapy; these patients have remained relapse-free up to 16.0+ months post-first SL-401 dose and up to 10.2+ months post-SCT. Median PFS had not been reached.

Of the 13 R/R patients evaluable for response, the ORR was 69%, and the CR rate was 31%.

3.8 Discussion and Rationale for Current Study

The rationale for clinical development of SL-401 for patients with AML or BPDCN is based on the high expression of the IL-3R on AML and BPDCN blasts, the potent preclinical activity of SL-401 against AML and BPDCN cells, the clinical responsiveness observed to date with SL-401, in BPDCN in particular, and the unmet medical need for these indications.

Clinical results with SL-401 indicate that the agent can be safely administered to patients with *de novo* AML, R/R AML, or BPDCN, with clinical benefit in terms of disease response and extended survival. While 16.6 µg/kg/day for 5 consecutive days was determined to be the MTD in Study 50047 and a safe starting dose for subsequent studies, the starting dose selected for this Phase 1/2 study, 7 µg/kg/day (similar to the lowest tested dose for this regimen (7.07 µg/kg/day) in Study 50047), allowed for an initial abbreviated (3 dose level) dose escalation/confirmation stage to an expected maximum tested dose (12 µg/kg/day) that appears to have the most favorable risk/benefit profile.

The SL-401 drug product used in the current study is manufactured using a commercial-scale process that will provide study material for all pivotal studies. Consequently, the purpose of the initial stage of the current study was to bridge the existing Phase 1/2 experience utilizing the earlier SL-401 drug product to SL-401 made using a commercial-scale manufacturing process. These initial clinical data will confirm the safety and activity of SL-401 from the commercial scale. Furthermore, the current study will generate clinical experience in which administration of multiple cycles of SL-401 can be evaluated in patient populations that may derive additional clinical benefit beyond administration of a single cycle.

The LFT and albumin findings from SL-401 in Study 50047 indicate that most patients with clinically meaningful changes in these parameters following administration of SL-401 would be expected to recover to near baseline levels by 3-4 weeks following the initiation of therapy. These results therefore support administration of cycles every 3 weeks with the allowance to delay the start of a subsequent cycle to allow toxicity resolution. This has been confirmed during Stage 1 of the current study, where the majority of patients have been able to receive multiple cycles of SL-401 despite transaminase elevations and hypoalbuminemia during Cycle 1. CLS was the principal DLT in Study 50047 and in the current study. Similarly, CLS is an event associated with treatment with approved doses of denileukin ditox (Ontak®), a Food and Drug

Administration (FDA)-approved treatment for patients with persistent or recurrent cutaneous T-cell lymphoma whose malignant cells express the IL-2 receptor. Treatment of patients with SL-401 at doses below those in which multiple cases of severe CLS were observed in Study 50047 is one element by which the risk of this SL-401-associated toxicity will be minimized in the current study.

During Study 50047, risk mitigation measures for CLS were implemented. These included premedication (e.g., an H₁-histamine antagonist, acetaminophen, and a corticosteroid); administration of IV albumin if serum albumin decreased to <3 g/dL; and a diuretic regimen (e.g., furosemide) if patients experienced >10% weight gain (with no hypotension) concurrent with the administration of a basal parenteral hydration to maintain intravascular volume. In the peri-treatment period, vital signs, weight, serum electrolytes, and albumin were monitored. Similar measures have been incorporated into the current study, as described in [Section 7.5.4](#). Additional precautions, including a requirement that patients have a normal cardiac ejection fraction at study entry, and requiring withholding of treatment in the setting of albumin reductions or weight increases during the dosing period, similar to recommendations concerning the optimal administration of denileukin diftitox, have also been implemented ([McCann et al. 2012](#), [Olsen et al. 2001](#), [Prince et al. 2009](#)).

Denileukin diftitox also is associated with loss of visual acuity, usually with loss of color vision, with or without retinal pigment mottling. Recovery was reported in some of the affected patients; however, most patients reported persistent visual impairment. This finding is considered related to the IL-2 component of denileukin diftitox. Although SL-401 targets IL-3R rather than IL-2R, patients will be monitored for potential vision loss in this study.

SL-401 was granted Breakthrough Therapy Designation (BTD) by the US FDA for the treatment of BPDCN in August 2016. In October 2016, the Sponsor conducted an interim analysis of efficacy data from 32 patients with BPDCN enrolled in this study between 06 October, 2014, and 29 August, 2016. A meeting was held with FDA on 20 December, 2016, to review the results of this interim analysis and discuss the continued development of SL-401 for treatment of BPDCN. As an outcome of that meeting, the following changes were made by Amendment 9:

- Enrollment of patients with AML is closed.
- Enrollment of patients with BPDCN is ongoing.
 - Any patient with first-line BPDCN enrolled in this study on or after 26 October, 2016, is included in Stage 3; a sufficient number of patients will be enrolled to ensure 10 evaluable patients are included, with evaluable patients being those with a diagnosis of BPDCN, as confirmed via central pathology review who received at least 1 dose of SL-401. These patients will constitute a standalone pivotal cohort for confirmation of efficacy of SL-401 in first-line BPDCN; for reference in this

protocol, this cohort will be designated Stage 3. The primary endpoint for this pivotal cohort is the CR rate.

- Any patients with R/R BPDCN enrolled in this study on or after 26 October, 2016, are allocated to Stage 4. After the maximum number of planned first-line BPDCN patients are enrolled in Stage 3, any additional first-line BPDCN patients are to be enrolled in Stage 4. BPDCN patients enrolled in Stage 4 subsequent to completion of enrollment in Stage 3 will receive the lyophilized formulation of SL-401 for Injection.
 - Enrollment will continue in Stage 4 until the study enrollment cap is reached.
- The total study sample size is increased to up to 120 patients (including ~70 patients with BPDCN) in order to adequately assess efficacy and safety of SL-401 in patients with BPDCN in a clinical study setting.
- The inclusion/exclusion criteria for patients with BPDCN and SL-401 dose and treatment schedule are the same across Stages 2-4, with the exception that only first-line BPDCN patients are eligible for Stage 3.
- Safety monitoring to assess visual acuity and color vision, which are potential class toxicities of immunotoxins, and follow-up to determine whether treatment with SL-401 alters the risk of veno-occlusive disease (VOD) after subsequent SCT have been added. Other study procedures and evaluations are the same across Stages 2-4.

Key elements included in Protocol Amendment 10 are as follows:

- The total study sample size is increased to up to 130 patients (including ~80 patients with BPDCN) in order to ensure continued access to SL-401 for BPDCN patients in a clinical study setting.
- Updated enrollment status.
- Updated guidance for toxicity management, including CLS management, to continue reducing the risk of severe CLS and other SL-401-associated toxicities.
- Updates to reflect agreements and requests made by the FDA, including agreements on the primary efficacy endpoint for Stage 3.

Protocol Amendment 11 provides for additional BPDCN patients to be enrolled in Stage 4.

Protocol Amendment 12 provides details on the timing of analyses of duration of response and overall survival for all cohorts, as well as modifications to certain procedures based on the approved package insert and follow up requirement for patients who received stem cell

transplant following treatment with SL-401, to identify engraftment delays or failures. SL-401 Injection frozen solution (1mg/mL) was approved by the Food and Drug Administration (FDA) on 21 December 2018 for the treatment of BPDCN in adults and in pediatric patients 2 years and older under the name ELZONRIS (tagraxofusp-erzs).

4 Study Objectives

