cells (Jordan, et al. 2006; Jordan, et al. 2000; Tehranchi, et al. 2010). Tagraxofusp is comprised of recombinant human IL-3 genetically fused to a truncated DT, in which the native receptorbinding domain of DT has been replaced with IL-3. The IL-3 domain of tagraxofusp is able to target the agent to cells that over-express IL-3R, leading to receptor-mediated endocytosis and localization of tagraxofusp to early endosomes. This allows tagraxofusp to kill cells in a distinct manner from other cancer therapeutics. First, tagraxofusp is a targeted therapy directed to the IL-3R that is differentially present on tumor bulk and/or CSCs versus normal hematopoietic stem cells. Second, tagraxofusp utilizes a payload that is not cell cycle-dependent. Therefore, it is designed to kill not just highly proliferative tumor bulk, but also relatively quiescent CSCs. Tagraxofusp utilizes a payload that may not be subject to multi-drug resistance mechanisms typically used by CSCs to evade traditional therapies. The payload also kills cells in a manner that is distinct from that of other available therapies, which is another reason why tagraxofusp is an effective addition to the therapeutic armamentarium against certain hematologic malignancies.

Tagraxofusp in frozen liquid formulation was approved by the US Food and Drug Administration (FDA) in 2019 for treatment of BPDCN in adults and pediatric patients 2 years and older based primarily on the efficacy findings from this study, STML-401-0114. STML401-0114 was designed as a Phase 1/2 dose escalation and expansion study targeting patients with BPDCN or AML. Stage 1 (dose escalation) enrolled patients with BPDCN, R/R AML, and previously untreated AML considered high risk for progression and/or unfit for standard therapy. Stage 2 (expansion) enrolled additional patients with first-line BPDCN, patients with R/R BPDCN, and R/R and untreated high risk AML patients. Stage 3 was a confirmatory cohort to test pre-specified hypotheses regarding the efficacy of tagraxofusp among first-line BPDCN patients in preparation for the biological licensing application (BLA) filing. Stage 4 initiated enrollment after August 29, 2016 through January 7, 2019 and included R/R BPDCN patients and first-line BPDCN patients enrolled after March 17, 2017. Patients enrolled into Stage 4 were treated with lyophilized formulation of tagraxofusp. At the time of BLA filing and approval limited data were available from Stage 4.

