1.1.2. Study Objectives

The following objectives are defined in the Study Protocol (Amendment 9, 09 February 2017). The response criteria referenced throughout the Study Objectives are provided in [Section 8](#).

Primary objectives for Stages 1, 2, 3, and 4 are as follows:

Stage 1: The objectives of Stage 1 are to:

- Determine the maximum tolerated dose (MTD), or the maximum tested dose where multiple dose limiting toxicities (DLTs) are not observed, of tagraxofusp.

Stage 2: The objectives of Stage 2 are to:

- Determine the efficacy of tagraxofusp in patients with BPDCN, as assessed by objective response rate (ORR).
- Characterize the safety profile of tagraxofusp at the MTD or maximum tested dose in both patients with AML and BPDCN.

Stage 3: The objectives of Stage 3 are:

- Determine the complete response (CR) rate (ie, CR + CR with incomplete blood count recovery [CRI] + CR [clinical] with minimal residual skin abnormality [CRC]) in patients with first-line BPDCN. Note that these objectives are supported by prespecified statistical hypotheses and were evaluated using appropriate statistical inference during the initial reporting of this study.
- Characterize the safety profile of tagraxofusp in patients with first-line BPDCN.

Stage 4: The objectives of Stage 4 are to:

- Further characterize the efficacy of tagraxofusp in first-line and R/R patients with BPDCN following the completion of Stage 2 and Stage 3 as assessed by the rate of CR (CR + CRI + CRC).
- Further characterize the safety profile of tagraxofusp among first-line and R/R patients with BPDCN.
- Characterize the efficacy and safety of a lyophilized formulation of tagraxofusp among first-line and R/R patients with BPDCN.

Secondary objectives include:

- Determine the CR rate (CR + CRI + CRC) for Stage 1 and 2 patients, and ORR for Stage 3 patients.

- Estimate duration of response (DOR), progression-free survival (PFS) and overall survival (OS) in patients with BPDCN. Note that for patients that received a stem cell transplant (SCT), duration of response includes time pre- and post-SCT.
- Enable preliminary characterization of the estimated ORR in patients with R/R AML, including subsets of patients with R/R AML categorized by pre-treatment blast counts, cytogenetics, or CD123 measurement.
- Estimate DOR, PFS, and OS in patients with AML.
- Characterize the pharmacokinetics (PK) and immunogenicity of tagraxofusp.

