4.4. Safety Analyses

With the exception of Subgroup Analyses ([Section 3.9](#)), all safety tabulations will be presented by disease (first-line BPDCN, R/R BPDCN, AML) for all patients in the Safety Population by stage of enrollment (all doses included). All safety tabulations will be presented for first-line BPDCN patients in the Safety Population who were treated at 12 µg/kg/day by stage of enrollment and for those treated with lyophilized formulation of tagraxofusp.

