Analysis of AEs over time will be conducted by presentation of AE incidence by cycle. For this analysis, incidence per cycle will be based on the onset of a particular preferred term event within the cycle, where onset is indicated by first or repeat occurrence or increase in severity of the event within that cycle. This analysis will be conducted for all AEs and for AEs of Grade ≥ 3 severity. For AEs of special interest, Kaplan-Meier analyses of time to first occurrence of Grade ≥ 2 severity will be conducted for FL BPDCN, R/R BPDCN, and AML patients.

AESI's will be determined using MedDRA version 19.0 standardized medical queries (SMQs), high-level terms, or preferred terms, as follows:

- Possible hypersensitivity events, based on the SMQ Hypersensitivity (broad search).

- Vascular capillary leak syndrome (CLS), based on the MedDRA SMQ [to be provided] in addition to preferred terms of hypoalbuminaemia, blood albumin decreased, and proteinuria.
- Visual acuity, based on the MedDRA preferred terms of visual acuity reduced, visual acuity reduced transiently, visual acuity tests abnormal.
- Post-transplantation veno-occlusive disease, based on the MedDRA preferred terms pulmonary veno-occlusive disease and veno-occlusive liver disease.
- Possible drug-induced liver injury events, based on the SMQ drug-related hepatic disorders (broad search).

Summary tables of AESIs produced will report AESI by preferred term, causality, severity grade, seriousness, and whether AESI led to discontinuation. These tabulations will be completed for all patients, by line of therapy for BPDCN patients, AML patients, and indication. AESIs will also be included in data listings.

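### Post-transplant VOD is tabulated over all treated patients, with no transplant-recipient denominator and no split at the amendments that introduced the follow-up

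*Protocol*

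**What the plan says.** Two follow-up requirements entered the protocol at different times.

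- **VOD.** Protocol 3.8, describing Amendment 9, says that "follow-up to determine whether treatment with SL-401 alters the risk of veno-occlusive disease (VOD) after subsequent SCT have been added". SAP 1.1.2 gives the date: "The following objectives are defined in the Study Protocol (Amendment 9, 09 February 2017".
- **Engraftment.** Describing Amendment 12, Protocol 3.8 adds a follow-up requirement for patients who had a stem cell "transplant following treatment with SL-401, to identify engraftment delays or failures". The documents give Amendment 12 no date, but the same paragraph reports that the frozen solution "was approved by the Food and Drug Administration (FDA) on 21 December 2018".

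The current text (Protocol 7.6.2 and 9.7) places both checks in survival monitoring, about every 90 days, with no restriction by stage. Protocol 10.1.1 makes VOD and engraftment delay or failure adverse events of special interest (AESIs).

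SAP 4.4.2 bases its adverse event analyses on events up to 30 days after the last dose. Its AESI list defines post-transplant VOD by two preferred terms and has no engraftment term. Of the AESI tables it says: "These tabulations will be completed for all patients, by line of therapy for BPDCN patients, AML patients, and indication". SAP 4.4 also asks for the safety tables in first-line patients at 12 µg/kg/day "by stage of enrollment and for those treated with lyophilized formulation of tagraxofusp". No table is restricted to transplant recipients, and no rule covers transplants done before the follow-up existed.

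On timing, Protocol 3.7.2 reports at the interim analysis "6 patients who sustained a remission while on SL-401 (CR [n=5]; PR [n=1]) and were then successfully bridged to SCT". SAP 1.1 says "Stage 4 initiated enrollment after August 29, 2016 through January 7, 2019".

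**The concern.** Post-transplant VOD can occur only in a patient who has had a transplant, and the follow-up was added to learn about risk after transplant. Dividing the events by all treated patients answers another question. The result moves with the transplant fraction, so two stages with the same per-transplant risk can show different rates.

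The second difficulty is ascertainment. Some transplants took place before sites were asked to look for VOD, and most before they were asked about engraftment. If later post-transplant events are added to the tables, the early transplants enter on a different basis from the later ones.

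The sponsor treats these events as important: they are AESIs, and Protocol 10.5 sends engraftment problems to 15-day reporting. Safety of the lyophilized product is a primary objective of Stage 4. A reader comparing columns could take a difference in transplant fraction or in follow-up for a difference in drug product.

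**Working it through.** The plan states no VOD rate, no engraftment rate and no total number of transplants, so there is no figure of its own to reproduce. The check is date arithmetic. The amendment history is used only to date the two requirements.

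**Inputs**

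- First-line patients at 12 µg/kg/day: 16 in Stages 1-2 (Protocol 3.7.2, evaluable), 13 in Stage 3 and 37 treated in Stage 4 (SAP 3.1); total 66.
- Transplants at the interim: 6 of 16 = 37.5%, after about 2-6 months of therapy. Another 5 of the 16 were still on treatment (Protocol 3.7.2).
- Stage 3 enrolment: 26 October 2016 to 17 March 2017, 142 days (SAP 3.1).
- First-line Stage 4 enrolment: after 17 March 2017 to 7 January 2019, 661 days (SAP 1.1).
- Amendment 9: 09 February 2017. Amendment 12: 21 December 2018 at the earliest. SAP 1.1 puts the approval in 2019; a later date only raises the shares in step 3.

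**Assumptions.** Enrolment is uniform within each window. Transplant comes 2, 4 or 6 months (60, 121 or 182 days) after the first dose. The transplant rate in Stages 3-4 equals the interim 37.5%. Transplants from Stages 1-2 before Amendment 9 number 6, or 11 if all 5 patients still on therapy were also transplanted by then.

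**Step 1, denominator.** All-patient rate / per-transplant rate = transplants / treated = 0.375 at the interim fraction. A per-transplant rate of 10% would show as 3.75% of treated patients.

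**Step 2, share before Amendment 9.** Amendment 9 falls 106 days into Stage 3 enrolment. With a 60-day lag, (106 - 60)/142 = 32% of Stage 3 transplants precede it; with 121 or 182 days, none do. No first-line Stage 4 transplant precedes it.

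- Total transplants: 6 + 0.375 × (13 + 37) = 24.75, or 11 + 18.75 = 29.75.
- Lowest share: 6/24.75 = 24%.
- Highest share: (11 + 0.375 × 13 × 0.324)/29.75 = 12.58/29.75 = 42%.

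**Step 3, share before Amendment 12.** 21 December 2018 falls 644 days into the first-line Stage 4 window. The Stage 4 shares before it are (644 - 60)/661 = 88%, (644 - 121)/661 = 79% and (644 - 182)/661 = 70%.

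- Lowest share: [6 + 0.375 × (13 + 37 × 0.699)]/24.75 = 20.57/24.75 = 83%.
- Highest share: [11 + 0.375 × (13 + 37 × 0.884)]/29.75 = 28.14/29.75 = 95%.

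**Step 4, sensitivity to the transplant rate.** With Stage 3-4 transplant rates from 20% to 50%, the share is 19-56% before Amendment 9 and 82-96% before Amendment 12. A majority before Amendment 9 needs a Stage 3-4 rate below 6/50 = 12% (14% with the 60-day lag) if there were 6 early transplants. With 11, it needs a rate below 11/50 = 22% (26% with the 60-day lag).

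**Step 5, precision.** With no events among n transplants, the exact two-sided 95% upper limit is 1 - 0.025^(1/n). This is 13.7% for n = 25, 17.6% for n = 19 (25 less the 6 early ones) and 45.9% for n = 6.

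**The case against.** **The tables as written stop at 30 days after the last dose.** On the current text that window is collected in every stage, so the change in follow-up hardly enters. This stands, and it rules out the inference that Stage 4 will show a higher VOD rate by construction. In addition, the SAP's planned pooling comparison is Stage 3 against Stage 4, and both fall largely or wholly after Amendment 9. It leaves the denominator problem untouched. It also means that events found by the post-transplant follow-up after day 30 reach no summary table.

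**Earlier transplants may have been captured anyway.** Protocol 7.6.2 applies the follow-up to any transplanted patient. The Amendment 12 wording can reach patients already transplanted, and data were cut on 13 March 2020 (SAP 3.13.4). Protocol 10.2 collects related events throughout follow-up and can be read as covering all serious ones. The 6 early recipients were counted as progression-free at the interim, hence alive. All this stands as a reason not to assume zero capture. It does not show full capture: no section tells sites to look back. Protocol 10 and 10.5 limit reporting beyond 30 days to related events, and the definition of related in 10.6 works against an event that a transplant readily explains. Earlier protocol versions are not available to settle it.

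**No engraftment rate is planned.** Correct, so no planned figure can be too low. The gap is that a protocol AESI has no SAP summary.

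**Conclusion.** The point holds as a reporting gap. The all-patient denominator understates the per-transplant VOD risk, by a factor of 0.375 if the interim transplant fraction applies. Once events from post-transplant monitoring are counted, Stages 1-2 are not ascertained on the same basis as Stages 3-4. At least 6 first-line transplants predate VOD follow-up, about 24-42% of those expected. Some 83-95% predate engraftment follow-up.

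The shares rest on uniform accrual, a 2-6 month lag, the 37.5% transplant rate and 21 December 2018 as the earliest Amendment 12 date. They cover first-line patients at 12 µg/kg/day only.

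A reader might infer three further things that the documents do not support:

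- That most transplants predate VOD follow-up. This would need a Stage 3-4 transplant rate well below the interim one.
- That reported rates are too low by a calculable amount. Multiplying a true rate by the share of later transplants assumes nothing was captured earlier. Missed events can only lower a rate, but how many were missed is unknown.
- That the aim of learning whether SL-401 alters VOD risk is a study objective lacking a comparator. It appears in the amendment history; Protocol 4.1-4.3 contain no VOD objective, and no comparative test is planned.

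**What to change.** Add one descriptive table to SAP 4.4.2:

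- Denominator: stem cell transplant recipients only.
- Outcomes: VOD, and engraftment delay or failure, using events recorded in post-transplant survival monitoring and not only those within 30 days of the last dose.
- Presentation: counts and rates with exact 95% intervals.
- Split: transplant before or after the relevant amendment (09 February 2017 for VOD; the Amendment 12 date, which the SAP should state, for engraftment).
- Earlier transplants with no documented check are shown as not ascertained, not as event-free.
- No stage or formulation comparison of these rates across the amendment dates.

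The cost is a paragraph of SAP wording and one table from data already collected. A new chart query after the March 2020 lock is not needed, nor is any change to Protocol 3.8. The downside is smaller denominators and wider intervals. With no events, leaving out 6 of 25 transplants raises the upper limit from 13.7% to 17.6%. The engraftment rate after Amendment 12 would rest on very few patients.
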